3.1.2 Study Procedures for All Cohorts

Patients will be required to provide sample tumor tissue showing the presence of CIS, to be obtained within 60 days prior to study entry. Tissue should be submitted as formalin-fixed paraffin-embedded (FFPE) blocks (blocks preferred) or at least 10 unstained slides, with an associated pathology report, for central testing. Patients with fewer than 10 unstained slides available at baseline (but no fewer than five) may be eligible following discussion with the Medical Monitor. The Sponsor may replace patients who are later found to be unevaluable for tumor PD-L1 expression by central testing.

Tumor response assessment via cystoscopy and urine cytology will occur every 12 weeks for the first 2 years, and every 24 weeks thereafter until 5 years, and then yearly.

A mandatory tissue biopsy will be obtained from all patients 6 months after C1D1 of atezolizumab. For patients in Cohort 1A, biopsies should be obtained up to 21 days prior to atezolizumab administration. For patients in Cohorts 1B, 2, and 3, biopsies should be obtained 14–21 days prior to BCG intravesical instillation (e.g., Weeks 10, 22, 46, 70 and 94; see [Appendix 3](#)).

The Sponsor may replace patients who are discontinued from the study before the required tumor biopsy samples are obtained.

At the 6-month timepoint (Week 24 visit), documentation of a complete response (CR) is required to continue on study treatment.

Definition of Complete Response (must meet all 3 criteria):

- Cytology: not positive (see below)
- Upper Urinary Tract Imaging (if performed): normal, or abnormal but supportive of CR (with non-positive selective ureteral cytologies)

- Cystoscopy: bladder appears normal; or bladder appears abnormal but all biopsies are negative; or any grade papilloma, any grade papillary urothelial neoplasm of low malignant potential (PUNLMP), or low grade pTa

Interpretation of Urine Cytology:

- If results are Unsatisfactory, Atypical Cell, Suspicious, or Indeterminate, then assay must be repeated no less than 24 hours and up to 21 days later.
- If the results are again Unsatisfactory or Atypical Cell (2 in a row), then treat as if the result was negative.
- Two consecutive Suspicious or Indeterminate urine cytology specimens require further evaluation by cystoscopy and/or upper tract imaging as deemed appropriate by the investigator
- If cytology results are Suspicious or Indeterminate and the biopsies are negative, then treat as if the result was negative
- All occurrences of positive urine cytology will require further evaluation by cystoscopy and/or upper tract imaging. A positive cytology result only indicates presence of disease and cannot be used alone to determine disease progression.

The date of a positive cytology result can be used for the date of recurrence, if the results of the cystoscopy, biopsy, or upper urinary tract assessment shows recurrence.

Patients with persistent and/or recurrent high grade NMIBC without progression (stage or grade progression of active disease, or the presence of new disease) at 12 weeks from treatment initiation may continue on study treatment.

Patients with recurrent low-grade papillary disease will be required to undergo resection with TURBT (unless medically contraindicated) and may continue on study and receive study treatment.

Indications for Discontinuation from Study for Disease Progression

- Stage or grade progression at any timepoint would require discontinuation from study therapy.
- Patients with persistent and/or recurrent high-grade NMIBC (any pT1, high grade pTa, or CIS) on or after the 6-month biopsy will be discontinued from study treatment and offered the option to undergo cystectomy or other bladder-sparing modalities as is clinically appropriate. Patients who undergo cystectomy will be requested to submit additional tissue from their cystectomy specimens.
- Patients with evidence of disease progression to muscle-invasive or metastatic disease at any timepoint will be discontinued from study treatment.

For all patients, additional evaluation (imaging, exam under anesthesia, biopsies) should be performed at investigator discretion for any of the following circumstances:

- Abnormal cystoscopy
- Positive urine cytology
- Two sequential suspicious or indeterminate urine cytology specimens

Study treatment with atezolizumab may be continued for a maximum of 32 q3w cycles or a total of 96 weeks of therapy. BCG treatment (induction and maintenance) may be continued for a maximum of 120 weeks (as clinically indicated; see [Appendix 3](#)). All study treatment will be discontinued in patients who undergo cystectomy or experience disease recurrence/progression or unacceptable toxicity, and in those who are not benefiting from study treatment (in the opinion of the investigator or the patient).

There may be circumstances in which either BCG or atezolizumab is permanently discontinued, but it may still be possible to continue the remaining study treatment with approval of the Medical Monitor. Patients in Cohorts 1B, 2, or 3 (atezolizumab plus BCG) who discontinue atezolizumab after receiving fewer than three cycles may be replaced.

All patients will be closely monitored for serious adverse events or protocol-defined events of special interest for 90 days or 30 days for adverse events, following their last dose of study therapy (atezolizumab and/or BCG) or initiation of non-protocol anti-cancer therapy, whichever occurs first. Safety assessments will include the incidence, nature, and severity of adverse events, changes in selected vital signs and laboratory abnormalities graded per NCI CTCAE v4.0.

Serum and plasma samples will be collected to monitor atezolizumab pharmacokinetics and to detect the presence of antibodies to atezolizumab.

Patient samples, including archival tumor tissues, as well as plasma, whole blood, and urine will be collected for future exploratory biomarker assessments.

A treatment completion/discontinuation visit will be performed for all patients within 30 days after the last administration of study treatment.

[figure not shown]
Patients who discontinue study treatment for a reason other than disease recurrence/progression or cystectomy (e.g., because of toxicity) will continue to undergo tumor assessments per protocol until they experience disease recurrence/progression or cystectomy, until the patient dies, withdraws consent, or until the study closes, whichever occurs first, for a maximum of 5 years after enrollment.

In addition, all patients will be followed for survival and subsequent anti-cancer therapy beginning 6 months after the treatment completion/discontinuation until loss to follow-up, death, withdrawal of consent, or study termination by the Sponsor, whichever occurs first, for a maximum of 5 years after enrollment.

Figure 6 presents the treatment plans for each cohort. The schedules of assessments are provided in Appendix 1 and Appendix 2.

[figure not shown]
Figure 6 Treatment Plans

Cohort 1A

Cohort 1A: Patients receive atezolizumab 1200 mg IV q3w.

Cohort 1B

[figure not shown]

BCG = bacille Calmette-Guérin.

Notes: Cohort 1B: During BCG Induction Course, patients receive atezolizumab 1200 mg IV q3w for a total of four doses plus BCG at the assigned dose weekly for a total of six doses. During BCG Maintenance Course 1, patients receive atezolizumab 1200 mg IV q3w for a total of four doses plus BCG at the assigned dose weekly for a total of three doses. OPTIONAL BCG Maintenance Courses 2-5, patients receive atezolizumab 1200 mg IV q3w for a total of eight doses per course plus BCG at the assigned dose weekly for a total of three doses per course. An optional collection of biopsy samples at disease progression/disease recurrence will be performed if clinically feasible.

Figure 6 Treatment Plans (cont.)

Cohorts 2 and 3

BCG = bacille Calmette-Guérin.

Notes: Cohorts 2 and 3: During BCG Induction Course, patients receive atezolizumab 1200 mg IV q3w for a total of four doses plus BCG at the assigned dose weekly for a total of six doses. During BCG Maintenance Course 1, patients receive atezolizumab 1200 mg IV q3w for a total of four doses plus BCG at the assigned dose weekly for a total of three doses. During BCG Maintenance Courses 2-5, patients receive atezolizumab 1200 mg IV q3w for a total of eight doses per course plus BCG at the assigned dose weekly for a total of three doses per course.

3.1.3 BCG Dose De-Escalation Scheme (Cohort 1B)

- This protocol will follow a 3 + 3 dose de-escalation scheme. MTD or MAD requires that either 0 of 3 or < 2 of 6 patients treated at a BCG dose level experience a DLT. If < 2 of 6 DLT-evaluable patients experience a DLT at the BCG dose level evaluated, that BCG dose level would be considered the MTD or MAD.
- A minimum of 3 patients will initially be treated at each BCG dose level evaluated.
- The following patients will not be considered evaluable for DLTs and will be replaced:

Patients who withdraw from either study treatment during the DLT assessment window (Days 1-21 of BCG Induction Course) for any reason other than a DLT

Patients who miss two or more doses of BCG or whose infusion of atezolizumab is delayed for ≥ 7 days during the DLT assessment window (Days 1-21 of BCG Induction Course) for any reason other than a DLT

Full-Dose BCG

Treatment starts at the full, standard doses of both BCG and atezolizumab:

- If 0 of 3 DLT-evaluable patients experience a DLT, MAD will be established and full-dose BCG and atezolizumab will be considered tolerable.

- If 1 of 3 DLT-evaluable patients experiences a DLT, 3 more patients will be enrolled at this dose level.
- If < 2 of 6 DLT-evaluable patients experience a DLT, MAD will be established, full doses of BCG and atezolizumab will be considered tolerable, and no BCG dose de-escalation will be implemented.
- If ≥ 2 of 3 or ≥ 2 of 6 DLT-evaluable patients receiving the full standard doses experience a DLT, the BCG dose will be reduced to 66% of full dose, and a minimum of 3 patients will be enrolled at 66% of full-dose level.

Sixty-Six Percent Dose Level of BCG

- If 0 of 3 DLT-evaluable patients experience a DLT, MTD will be established and the 66% of full BCG dose and atezolizumab will be considered tolerable.
- If 1 of 3 DLT-evaluable patients experiences a DLT, 3 additional patients will be enrolled at this dose level.
- If < 2 of 6 DLT-evaluable patients experience a DLT, MTD will be established as 66% of full dose BCG and full dose atezolizumab.
- If ≥ 2 of 3 or ≥ 2 of 6 DLT-evaluable patients receiving 66% of a full BCG dose experience a DLT, the BCG dose will be reduced to 33% of a full dose, and a minimum of 3 patients will be enrolled at the 33% of full dose level.

Thirty-Three Percent Dose Level of BCG

- If 0 of 3 DLT-evaluable patients experience a DLT, MTD will be established and the 33% of full BCG dose and atezolizumab will be considered tolerable.
- If 1 of 3 DLT-evaluable patients experiences a DLT, 3 additional patients will be enrolled at this dose level.
- If < 2 of 6 DLT-evaluable patients experience a DLT, MTD will be established as 33% of full-dose BCG and full-dose atezolizumab.
- If ≥ 2 of 3 or ≥ 2 of 6 DLT-evaluable patients receiving the 33% of a full BCG dose experience a DLT at this dose level, this dosing schedule of combination BCG (33%) and atezolizumab will be considered intolerable, and Cohort 1B will be closed.
- BCG dose levels will be evaluated as described above until the MTD or MAD has been determined, or until the last of the BCG dose levels has been evaluated. For patients in Cohort 1B, if 33% of a full BCG dose is determined to be intolerable in combination with atezolizumab and further therapy with BCG is not permitted, patients may be allowed to continue in the study with single-agent atezolizumab 1200 mg IV q3w (for a total of 96 weeks)
- No atezolizumab dose reductions will be permitted.

On the basis of a review of available safety and PK data during this and other studies with both agents, BCG dose de-escalation may be halted or modified by the Sponsor in consultation with the Study Investigators and/or Steering Committee.

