Cohort 1B will commence enrollment once 3 patients in Cohort 1A have completed one cycle (21 days) of study therapy. Cohort 1B will evaluate the safety and tolerability, DLTs, and MTD or MAD of the combination of atezolizumab and BCG in patients with BCG-unresponsive NMIBC. Data from Cohort 1B will be used to inform on the safety and tolerability of combination treatment in NMIBC, as determined at the MTD or MAD, as well as the recommended starting BCG dose in Cohorts 2 (BCG-relapsing NMIBC) and 3 (VHR BCG-naive NMIBC). Approximately 8–18 patients will be enrolled into Cohort 1B. If fewer than 8 patients are required to establish MTD or MAD in this cohort, additional patients will be enrolled for a minimum of 8 patients in this cohort.

- Cohort 1 Expansion

An expansion cohort will allow enrollment of up to approximately 10 additional patients from Cohorts 1A or 1B. The purpose of this expansion cohort is to provide additional safety and efficacy data on these patients, depending on the safety profile observed in Cohort 1B. If few or no DLTs are observed with the combination of atezolizumab and BCG, additional Cohort 1B patients will be enrolled to better characterize the safety clinical activity of combination therapy. Alternatively, if the combination of atezolizumab and BCG is deemed intolerable in the Cohort 1B population, additional Cohort 1A patients will be enrolled to provide additional safety and efficacy data for atezolizumab monotherapy in the BCG-unresponsive patients.

Enrollment into Cohorts 2 and 3 will not begin until safety and preliminary anti-tumor activity results from approximately 20 patients across Cohort 1 (1A and 1B) are obtained and the preliminary benefit/risk has been evaluated.

- Cohort 2

Cohort 2 will commence once the preliminary risk/benefit assessment from Cohorts 1A and 1B has demonstrated an acceptable safety and efficacy profile. Cohort 2 will evaluate the safety, tolerability and preliminary efficacy of the combination of atezolizumab and BCG (dosed at the MAD or MTD defined by Cohort 1B) in patients with BCG-relapsing NMIBC. Approximately 10 patients will be enrolled into Cohort 2.

[figure not shown]
- Cohort 3

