de-escalation scheme evaluating up to three dose levels of BCG until the BCG MTD (or MAD) for the two-drug combination in BCG-unresponsive NMIBC is defined. The dose of atezolizumab will be fixed; dose de-escalation will occur only for BCG. The three BCG dose levels to be evaluated in Cohort 1B will be the full BCG dose (with a starting dose of 50 mg), followed by 66% of a full BCG dose (33 mg), followed by 33% of a full BCG dose (16.5 mg) [Cohort 1B only]. In the first course, patients will receive concurrent atezolizumab + BCG at the assigned dose. The MTD or MAD will be determined on the basis of DLTs observed during the DLT assessment window (defined as Days 1–21 of BCG Induction Course). After the MTD or MAD is determined for Cohort 1B, this dose will be used for all subsequent patients enrolled into Cohorts 1B, 2, and 3, unless the MTD is determined to be 33% of a full BCG dose. If MTD is determined to be 33% of a full BCG dose, then, no patients will be enrolled into Cohorts 2 and 3 until an assessment of the safety and activity of the combination of atezolizumab plus 33% of a full BCG dose is completed. Atezolizumab plus 33% of a full dose will not be carried into Cohorts 2 and 3 unless a favorable risk-benefit profile is demonstrated. If MTD or MAD is reached before 8 patients have been enrolled in Cohort 1B, additional patients will be enrolled up to a minimum of 8 total patients. These additional patients will be treated at the established MTD or MAD. See Section 3.1.3 for a description of the BCG dose de-escalation scheme and Section 3.1.4 for the definition of DLT.

A minimum of 3 patients will be enrolled into each BCG dose level evaluated. However, for the starting dose level in Cohort 1B, dosing of the second and third patients will be staggered by a minimum of 1 week relative to the first patient. If the first patient does not experience unacceptable toxicity during the first week of combination treatment, the second and third patients at the first dose level may start combination treatment without delay. Dosing for subsequent dose levels will not be staggered.

The treatment regimen for Cohort 1B patients is as follows (see [Figure 6](#)):

BCG

- BCG Induction Course (12 weeks): BCG induction will begin on study Day 1. BCG will be administered at the assigned dose (see Section 3.1.3) weekly for a total of six doses (BCG induction).

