investigator to be clinically insignificant, and that returns to Grade ≤ 2 within 14 days with treatment interruption

Grade 3 arthralgia that can be adequately managed with supportive care or that resolves to Grade ≤ 2 within 7 days

Grade 3 fever (in the absence of any clinically significant source of fever) that resolves to Grade ≤ 2 within 7 days with supportive care

Grade 3 laboratory abnormality that is asymptomatic and deemed by the investigator not to be clinically significant

Grade 3 autoimmune thyroiditis or other endocrine abnormality that can be managed by endocrine therapy that would not necessitate initiation of systemic corticosteroids

All DLTs must be reported via the paper Serious Adverse Event/Adverse Event of Special Interest Reporting Form (see Section 5.3). All DLTs will be considered adverse events of special interest for this protocol and must be reported to the Sponsor in an expedited manner, as indicated in Section 5.4.

BCG dose de-escalation decisions will be made by the Sponsor in consultation with the Study Investigators and/or the Steering Committee after review of available relevant data. See Section 4.5, Appendix 1, and Appendix 2 for the schedule of study assessments.

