Grade 3/4	
 Withhold atezolizumab. Consider starting 10 mg/day oral prednisone or equivalent, with taper over 1–2 weeks. Resume atezolizumab if symptoms resolve and corticosteroid dose is equivalent to 10 mg/day. Refer to the TICE prescribing information for additional management guidelines pertaining to BCG.
Fever	
< 101° F (38.3° C)	
 Continue atezolizumab and BCG (patients receiving induction or maintenance BCG at time of symptom) Treat symptoms with non-steroidal anti-inflammatory drugs (e.g., ibuprofen). Withhold BCG and atezolizumab.
$\geq 101^{\circ}$ F (38.3° C)	
 For fever < 24 hours, and in absence of other new grade ≥ 2 symptoms, evaluate and rule out co-existing infection including urine and blood culture, blood tests, and chest X-ray. Consider consultation with infectious disease specialist. For fever > 24hours, would recommend immediate consultation with infectious disease specialist, discontinuation of BCG instillations, urine and blood culture, blood tests, and chest X-ray. Consider initiation of ≥ 2 antimicrobial agents including coverage with anti-tuberculosis therapy while diagnostic evaluation is being conducted. Refer to the TICE prescribing information for additional management guidelines pertaining to BCG.
Local bladder symptoms	
Dysuria	
 Refer to the TICE prescribing information for management guidelines pertaining to BCG.
Frequency	
 Refer to the TICE prescribing information for management guidelines pertaining to BCG.
Hematuria	
 Refer to the TICE prescribing information for management guidelines pertaining to BCG.
Local inflammation (e.g., epididymitis, prostatitis, orchitis)	
 Refer to the TICE prescribing information for management guidelines pertaining to BCG.

BCG = bacille Calmette-Guérin; GGO = ground-glass opacity; IV = intravenous; LFT = liver function test; TNF- α = tumor necrosis factor- α ; TSH = thyroid-stimulating hormone; ULN = upper limit of normal.

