6.1 DETERMINATION OF SAMPLE SIZE

The sample sizes for Cohorts 1A, 2, and 3 were based on clinical and operational considerations. The sample size for Cohort 1B was based on a 3+3 dose de-escalation design appropriate for assessing DLTs and MTD or MAD of BCG in combination with atezolizumab.

An evaluation of results from Cohorts 1A and 1B will be performed prior to initiation of enrollment in Cohorts 2 and 3. [Table 11](#) shows the 95% CI for selected observed CR rates for a range of sample sizes for Cohorts 1A and 1B pooled.

Table 11 95% CI for Selected Observed 6-Month Complete Response Rates in Cohorts 1A and 1B

Cohort	N	Number of Patients with CR (Observed CR Rate)	95% CI for CR Rate ^a
Cohorts 1A and 1B pooled	12	5 (42%)	(15%, 72%)
		6 (50%)	(21%, 79%)
	15	6 (40%)	(16%, 68%)
		7 (47%)	(21%, 73%)
	20	8 (40%)	(19%, 64%)
		9 (45%)	(23%, 68%)

CR = complete response.

^a Clopper-Pearson method.

[Table 12](#) shows the 95% CI for selected observed CR rates with the planned maximum enrollment of patients in either Cohorts 2 or 3.

Table 12 95% CI for Selected Observed 6-Month Complete Response Rates with the Planned Maximum Enrollment of Patients in Either Cohort 2 or 3

Cohort	N	Number of Patients with CR (Observed CR rate)	95% CI for CR Rate ^a
Cohorts 2 or 3	20	10 (50%)	(27%, 73%)
		12 (60%)	(36%, 81%)
		14 (70%)	(46%, 88%)
		16 (80%)	(56%, 94%)
		18 (90%)	(68%, 99%)

CR = complete response.

^a Clopper-Pearson method.

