NEUROLOGIC DISORDERS

Myasthenia gravis and Guillain-Barré syndrome have been observed with single-agent atezolizumab. Patients may present with signs and symptoms of sensory and/or motor neuropathy. Diagnostic work-up is essential for an accurate characterization to differentiate between alternative etiologies. Management guidelines for neurologic disorders are provided in [Table 10](#).

Table 10 Management Guidelines for Neurologic Disorders

Event	Management
Immune-mediated neuropathy, Grade 1	
 • Continue atezolizumab. • Investigate etiology.
Immune-mediated neuropathy, Grade 2	
 • Withhold atezolizumab for up to 12 weeks after event onset. ^a • Investigate etiology. • Initiate treatment as per institutional guidelines. • If event resolves to Grade 1 or better, resume atezolizumab. ^b • If event does not resolve to Grade 1 or better while withholding atezolizumab, permanently discontinue atezolizumab and contact Medical Monitor. ^c
Immune-mediated neuropathy, Grade 3 or 4	
 • Permanently discontinue atezolizumab and contact Medical Monitor. ^c • Initiate treatment as per institutional guidelines.
Myasthenia gravis and Guillain-Barré syndrome (any grade)	
 • Permanently discontinue atezolizumab and contact Medical Monitor. ^c • Refer patient to neurologist. • Initiate treatment as per institutional guidelines. • Consider initiation of 1–2 mg/kg/day oral or IV prednisone or equivalent.

^a Atezolizumab may be withheld for a longer period of time (i.e., > 12 weeks after event onset) to allow for corticosteroids (if initiated) to be reduced to ≤ 10 mg/day oral prednisone or equivalent. The acceptable length of the extended period of time must be agreed upon by the investigator and the Medical Monitor.

^b If corticosteroids have been initiated, they must be tapered over ≥ 1 month to ≤ 10 mg/day oral prednisone or equivalent before atezolizumab can be resumed.

^c Resumption of atezolizumab may be considered in patients who are deriving benefit and have fully recovered from the *immune-mediated* event. Patients can be re-challenged with atezolizumab only after approval has been documented by both the investigator (or an appropriate delegate) and the Medical Monitor.

Appendix 12

Risks Associated with Atezolizumab and Guidelines for Management of Adverse Events Associated with Atezolizumab (cont.)

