IMMUNE-MEDIATED MENINGOENCEPHALITIS

Immune-mediated meningoencephalitis is an identified risk associated with the administration of atezolizumab. *Immune-mediated* meningoencephalitis should be suspected in any patient presenting with signs or symptoms suggestive of meningitis or encephalitis, including, but not limited to, headache, neck pain, confusion, seizure, motor or sensory dysfunction, and altered or depressed level of consciousness. Encephalopathy from metabolic or electrolyte imbalances needs to be distinguished from potential meningoencephalitis resulting from infection (bacterial, viral, or fungal) or progression of malignancy, or secondary to a paraneoplastic process.

All patients being considered for meningoencephalitis should be urgently evaluated with a CT scan and/or MRI scan of the brain to evaluate for metastasis, inflammation, or edema. If deemed safe by the treating physician, a lumbar puncture should be performed and a neurologist should be consulted.

Patients with signs and symptoms of meningoencephalitis, in the absence of an identified alternate etiology, should be treated according to the guidelines in [Table 11](#).

Table 11 Management Guidelines for *Immune-Mediated* Meningoencephalitis

Event	Management
Immune-mediated meningoencephalitis, all grades	
 • Permanently discontinue atezolizumab and contact Medical Monitor. ^a • Refer patient to neurologist. • Initiate treatment with 1–2 mg/kg/day IV methylprednisolone or equivalent and convert to 1–2 mg/kg/day oral prednisone or equivalent upon improvement. • If event does not improve within 48 hours after initiating corticosteroids, consider adding an immunosuppressive agent. • If event resolves to Grade 1 or better, taper corticosteroids over ≥ 1 month.

^a Resumption of atezolizumab may be considered in patients who are deriving benefit and have fully recovered from the *immune-mediated* event. Patients can be re-challenged with atezolizumab only after approval has been documented by both the investigator (or an appropriate delegate) and the Medical Monitor.

RENAL EVENTS

Immune-mediated nephritis has been associated with the administration of atezolizumab. Eligible patients must have adequate renal function. *Renal* function, including serum creatinine, should be monitored throughout study treatment. Patients with abnormal renal function should be evaluated and treated for other more common etiologies

Appendix 12

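### In Cohort 1B, patients taken off study drug in Days 1–21 by toxicity that falls short of a DLT are replaced, so the 3+3 tolerability count leaves them out

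*Combined protocol and SAP*

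**What the plan says.** Section 6.1 gives the basis of the cohort: "The sample size for Cohort 1B was based on a 3+3 dose de-escalation design appropriate for assessing DLTs". Section 3.1.3 accepts a BCG dose level when no DLT is seen in 3 evaluable patients, or fewer than 2 in 6.

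Two groups are unevaluable and replaced, in each case unless the cause is a DLT:
- "Patients who withdraw from either study treatment during the DLT assessment window" (Days 1–21);
- patients who miss at least two BCG doses in the window, or whose atezolizumab infusion is delayed by 7 days or more.

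Section 3.1.4 defines a DLT by grade and, for some events, duration. Having to stop a drug is not a criterion.

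Appendix 12 separately says when atezolizumab must end. For several events that may sit below those limits the instruction is "Permanently discontinue atezolizumab and contact Medical Monitor". Section 4.6.2 also requires discontinuation for intolerable toxicity related to atezolizumab or the combination, with no grade attached. Section 5.1.3 requires BCG to be withheld for as long as a patient is on systemic corticosteroids.

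**The concern.** The protocol has two sets of rules for the same patient. The safety rules say the patient cannot continue the regimen. The evaluability rule removes that patient from the count that decides whether the regimen is tolerable. Replacement then depends on drug-related toxicity, and the patients who remain are those who stayed on treatment.

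Determining the MTD, or tolerability at the MAD, is the second safety objective in Section 2.1. The result sets the BCG dose for later Cohort 1B patients and, with a special condition only for the 33% level, for Cohorts 2 and 3. Section 1.4 says that toxicity allowed in metastatic disease would not be acceptable in this early setting.

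**Working it through.** **1. The plan's own figure.** Three BCG levels × 6 evaluable patients = 18, the upper end of the 8–18 in Section 3.1.1. The overall total also agrees: 12 + 18 + 10 + 10 + 10 + 10 = 70. The 18 counts evaluable patients. If a fraction q is replaced, 18 evaluable patients need 18/(1 − q) treated: 20.0 at q = 10%, 22.5 at q = 20%.

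**2. The passages side by side.**

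| Event | Appendix 12: permanent stop | Section 3.1.4: DLT limit | What falls between |
|---|---|---|---|
| Hepatic (Table 2) | Grade 3 or 4, no duration | Grade ≥3 for >48 h (symptomatic) or >72 h (asymptomatic) | Shorter events |
| Myasthenia gravis, Guillain-Barré (Table 10) | Any grade | Grade ≥3 | Grades 1–2 |
| Meningoencephalitis (Table 11) | All grades | Grade ≥3 | Grades 1–2 |
| Suspected HLH/MAS (Table 14) | No grade stated | Grade ≥3, or the hematologic limits | Anything below those |

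**3. The missed-dose route.** Appendix 3 places BCG at Weeks 0, 1 and 2 within Days 1–21. Appendix 12 starts prednisone for a Grade 2 pulmonary event, which is below the Grade ≥3 limit. If this happens before the Week 1 instillation and treatment lasts past Week 2, two BCG doses are missed and the patient is replaced.

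**4. The date of withdrawal.** Appendix 3 places atezolizumab at Weeks 0 and 3, so only one infusion falls in the window. The protocol does not say whether withdrawal is dated at the event, the decision or the first omitted infusion. If it is dated after Day 21, the patient stays evaluable and scores as having no DLT. On either dating the event is not counted.

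**5. Effect on the decision.** Let p be the chance of a DLT and q the chance that a patient leaves the count through treatment-related toxicity short of a DLT, the two being mutually exclusive. The documents give neither, so both are assumptions. A level passes with probability

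A(r) = (1 − r)³ + 3r(1 − r)⁵.

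As written, r = p/(1 − q). If the q events counted, r = p + q.

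| p | q | As written | If counted |
|---|---|---|---|
| 0% | 5% | 100% | 97.3% |
| 0% | 10% | 100% | 90.6% |
| 10% | 5% | 89.7% | 81.4% |
| 10% | 10% | 88.7% | 70.9% |
| 10% | 20% | 86.2% | 49.4% |

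Example, third row: r = 0.10/0.95 = 0.105 gives 0.897; r = 0.15 gives 0.814. With p = 0 no value of q can fail a level as written. At q = 20%, the chance of two or more such events in 6 treated patients is 34.5%.

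**6. A rough scale from the documents.** Table 3 gives withdrawal for any adverse event as 2.9% to 5.9% in three metastatic monotherapy groups over all of treatment. Putting those in as q, with p = 0:
- A(0.029) = 0.971³ + 3 × 0.029 × 0.971⁵ = 0.991
- A(0.059) = 0.941³ + 3 × 0.059 × 0.941⁵ = 0.964

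The gap from 100% is then about 1 to 4 percentage points. These rates cover all causes and far more than 21 days, but they exclude BCG, so they bound nothing for the combination.

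**The case against.** **Safeguards exist.** The sponsor takes de-escalation decisions with the investigators or Steering Committee on all relevant data and may halt or modify the scheme (Sections 3.1.3, 3.1.4). Guillain-Barré syndrome, myasthenia gravis, meningoencephalitis and hepatitis are events of special interest reportable within 24 hours (Section 5.2.3). An iDMC meets about every 4 months (Section 3.2), and safety summaries cover all treated patients (Section 6.5). This stands as mitigation. None of it says how these patients enter the dose decision, and Section 6.5 lists DLTs only for evaluable patients.

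**The events are probably uncommon.** None of the 16 withdrawals itemised for 429 IMvigor210 patients belongs to the four event groups in the table under step 2. This also stands, for monotherapy.

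Several stronger inferences are not supported:
- *All treatment-ending immune toxicity is lost.* Most non-hepatic toxicity of Grade 3 or above is already a DLT.
- *The rate of DLTs as defined is understated.* Among evaluable patients it is p/(1 − q), slightly above p. What is understated is the share who could not tolerate the regimen, p + q.
- *Fever is another mandated stop.* For fever beyond 24 hours Table 8 in Section 5.1.3 only recommends "discontinuation of BCG instillations".
- *The 2.5% rate of related Grade 3–4 ALT increase (Section 1.3.4) sizes the gap.* It gives 1 − 0.975⁶ = 14.1% for at least one in 6, but events lasting beyond 48 or 72 hours are DLTs and are counted. The larger cohort's 1.3% gives 1 − 0.987⁶ = 7.5%.
- *Cohorts 2 and 3 rest on 3 to 6 patients.* Cohort 1B enrols at least 8, and benefit-risk in about 20 Cohort 1 patients is reviewed first (Sections 1.4, 3.1.1).

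Re-challenge with approval is possible for most of these events, but it does not restore evaluability in the window.

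**Conclusion.** The contradiction is in the text. Sections 3.1.3 and 3.1.4 and Appendix 12 together allow a patient to be taken off atezolizumab permanently for treatment-related toxicity and then be replaced as uninformative about tolerability. The direction is clear: a level passes more readily than it would if these patients counted. The size is not known. It runs from about 1 point (q = 2.9%, p = 0) to about 37 points (q = 20%, p = 10%: 86.2% against 49.4%), and the upper values of q are assumptions well above the monotherapy withdrawal rates quoted.

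The calculation assumes independent patients, mutually exclusive p and q, and strict use of the 3+3 count without discretionary override. The documents do not show that any patient was replaced for this reason or that any dose was wrongly accepted. The matter merits correction because the count feeds a stated objective and the repair is inexpensive.

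**What to change.** Reconcile Sections 3.1.3 and 3.1.4 with Sections 4.6.2 and 5.1.3 and Appendix 12:
- A patient who stops or misses study drug in the window because of treatment-related toxicity, under the protocol's own guidance, should not be replaced without comment.
- Define the date of withdrawal relative to Day 21.
- State in advance how such patients enter the dose-level decision.
- Report their number beside the DLT count for each dose level.
- Check whether any Cohort 1B patient was replaced for this reason and, if so, show the count with and without that patient.

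Which events should be dose-limiting, and when treatment should stop, is left to the sponsor.

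The cost is wording and a short data check. The tolerability count may look slightly less favourable. Further patients could be needed under the existing 3+3 rules, since one counted event in 3 adds 3 patients and two open a lower level with at least 3 more.
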